8.1.5. Post-Injection Systemic Reactions

Summaries of post-injection systemic reactions that occur on the day of an injection or within 3 days after an injection will be presented by treatment group, by the first six injections and over all injections, and PT for the following:

- Post-Injection Systemic Reactions Adverse Events of Special Interest by Category and PT [T13.33, T23.32].
- Serious Post-Injection Systemic Reactions Adverse Events of Special Interest by Category and PT [T13.34, T23.33].
- Post-Injection Systemic Reactions per Anaphylactic Reaction CMQ broad search (on the day of the injection or within 3 days after the Belimumab injection) by PT in the first six injections [On treatment:T13.35].
- Serious Post-Injection Systemic Reactions per Anaphylactic Reaction CMQ broad search (on the day of the injection or within 3 days after the Belimumab injection) by PT in the first six injections [on Treatment: T13.36].
- Serious Acute Post-Injection Systemic Reactions/Hypersensitivity per GSK Adjudication by PT in the First Six Injections [On Treatment: T13.37].
- Serious Delayed Acute Hypersensitivity Reactions per GSK Adjudication by PT in First Six Injections [On Treatment:T13.38].
- Serious Delayed Non-Acute Hypersensitivity Reactions per GSK Adjudication by PT in First Six Injections [On Treatment: T13.39].
- Post-Injection Systemic Reactions per Anaphylactic Reaction CMQ broad search (on the day of the injection or within 3 days after the Rituximab infusion) by PT [On treatment:T13.40].

8.1.6. Additional Adverse Event Summaries to Assess the Impact of the Coronavirus Disease 2019 (COVID-19) Pandemic

Additional adverse event summaries will be produced to further understand the safety profile and/or impact of the COVID-19 pandemic on safety.

Two listings will be produced to show the number of subjects with a suspected, probable or confirmed COVID-19 infection. The first listing will present data for Year 1 On Treatment (Section 5.12) [L13.26]; the second listing will present data for Years 1 and 2 combined On-Study (Section 5.11) [L23.27]. Both listings will also show the number of subjects who had a COVID-19 diagnosis test performed and the number of subjects with positive, negative, or indeterminate results. The listings will be based on information collected on the COVID-19 Coronavirus Infection Assessment CRF page.

Extra tables will be produced to display the incidence of Adverse Events over the time course of the trial. Event rates will be reported by calendar time defined as either pre or during the COVID-19 pandemic (or post the pandemic if applicable by the Year 2 reporting). The COVID-19 environment onset date will be used to define pre and during the COVID-19 pandemic (Section 15.6.16).

The following Tables will summarise the Year 1 On Treatment (Section 5.12) events for pre or during the COVID-19 pandemic. Event rates will be adjusted for on treatment exposure (Section 15.6.2, On -Treatment exposure in the relevant pandemic phase (Year 1)).

- The overall rates of AEs, SAEs and severe AEs [T13.49]
- The overall rates of AEs, SAEs and severe AEs, presented by Country Region (USA/Canada vs. Europe vs. Rest of World) (Section 5.5.2.) [T13.50]
- The most frequent Adverse Events ($\geq 5\%$ incidence in any treatment group) by Preferred Term [T13.51]

The following Tables will summarise the Year 1 and 2 combined On-Study (Section 5.11) events for pre or during the COVID-19 pandemic. Note that if a date is defined prior to the Year 2 reporting for the 'end of the pandemic' then this output will split events into pre, during or post the COVID-19 pandemic. Event rates will be adjusted for on-study exposure in the relevant pandemic phase (Section 15.6.2, On-Study exposure (Years 1&2 combined)).

- The overall rates of AEs, SAEs and severe AEs [T23.42]
- The overall rates of AEs, SAEs and severe AEs, presented by Country Region (USA/Canada vs. Europe vs. Rest of World) (Section 5.5.2.) [T23.43]
- The most frequent Adverse Events ($\geq 5\%$ incidence in any treatment group) by Preferred Term [T23.44]

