Randomization and the first dose of belimumab should be completed within 35 days of initiation of screening procedures. Participants will be receiving stable standard therapy at entry. At randomization, participants will be stratified by their screening SLEDAI-2K score (≤9 vs. ≥10), by immunosuppressant use at screening (immunosuppressant use vs. no use) and by screening corticosteroid dose (prednisone equivalent ≤10 mg/day vs. >10 mg/day). Belimumab will be administered SC on Day 1 and then weekly (i.e., every 7 days ±1 day) through Week 51 for Arms A and B, and through Week 103 for Arm C. SC injections will be administered at alternating injection sites between the left or right thighs and the abdomen. Rituximab-placebo or rituximab will be administered by intravenous (IV) infusions at Weeks 4 and 6 for Arms A and B. Participants in Arms A and B will be administered a pre-medication regimen 30 minutes before each rituximab-placebo or rituximab infusion on Weeks 4 and 6, including methylprednisolone 100 mg IV or equivalent, an antihistamine, and acetaminophen or equivalent.

Participants in any arm who are deemed treatment failures for efficacy endpoints at any time during the study will be encouraged to remain in the study and continue to have all efficacy and safety assessments.

Participants randomized to Arms A or B who enter the study on immunosuppressants will discontinue immunosuppressants prior to or on the day of the Week 4 visit. Continuing the stable immunosuppressant dose until Week 4 allows participants to receive 3 weeks of belimumab SC prior to discontinuing their immunosuppressants. Corticosteroids may be adjusted as necessary during this transition period. If participants in Arms A and B receive immunosuppressants after the Week 4 visit they will be deemed treatment failures. Participants in Arm C will continue their stable immunosuppressants throughout the study at the discretion of the investigator. If participants in Arm C require an increased dose of their stable immunosuppressant after Week 12 or addition of a new immunosuppressant they will be considered a treatment failure.

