- Procedures to be performed at Unscheduled Visits are based on reason for Unscheduled Visit, including adverse event or discontinuation of study agent. Please refer to Section 9.4 and to the guidance provided in the Study Reference Manual.
- m. The interim medical history, including SLE medications, should be reviewed prior to randomization to assure that the participant's eligibility has not changed.
- n. Blood samples for a B cell receptor analysis should be obtained in the event of a suspected SLE Flare (refer to footnote q).
- o. To be conducted at US sites only.
- p. To be conducted only at US study sites.
- q. To be conducted only at US study sites. B-cell receptor samples are also collected at US sites when subjects experience a suspected SLE Flare.
- r. Separate Genetics informed consent as needed per country specific requirements. Genetics informed consent and sample can be obtained any time after baseline.
- s. If a subject happens to be scheduled for an infusion (week 4 and/or 6) on the same day of the week as their normally scheduled belimumab injection, whenever possible, the day of the belimumab injection should be altered within the dosing window to separate the day of the injection from the day of the infusion to allow for appropriate safety monitoring of the infusion. If subject has already self-administered the belimumab dose on the day of IV infusion, contact study Medical Monitor for guidance prior to administering the rituximab/rituximab-placebo dose.
- t. Independent assessor will perform symptom-driven physical examination to include, at a minimum, assessments of eyes, mouth, skin, lungs, cardiovascular system, abdomen, and extremities (including joints). Independent assessors must have a source document (paper record in the study file) where the findings in the clinical exam and laboratory analyses supporting the scoring of S2K are described.
- u. To be conducted only at select European sites

Table 2 Double-blind Observational Phase Procedures: Year 2, Arms A and B

		Observ	vational Perio	d – Arms A	and B (a)				
Arms A and B Double-blind Observational Phase Procedures (W=Week)	W60	W64	W72	W80	W88, W96	W104	Unscheduled Visit (e)	Early Withdrawal Visit (f)	Follow-up visit (8 weeks post last dose) (j)
Assessments: Clinic									
Symptom-driven physical exam, vital signs	Х	Χ	Χ	Х	X	Х	Х	Χ	Х
Weight						X		Χ	
Assessments: Independent Assessor									
SLEDAI-2K: Blinded Assessor (m)		Χ		Χ		X	X	Χ	

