| 23.25. | NEW | ITT | Study Treatment Related Serious Fatal and Non-Fatal Adverse Events by PT – Both Belimumab and Rituximab [1] - On Study (Year 1&2) | 
 New output (required for Plain Language Summary) |
| Survival Status | | | | |
| 23.26. | 23.29 | ITT | Survival Status at Week 104 | |
| Adverse Events of Special Interest (AESI) | | | | |
| 23.27. | 23.30 | ITT Year 2 | Adverse Events of Special Interest by Category - On Study (Year 2) | 
 Use new 'ITT Year 2' Population defined in Section 2.2. |
| 23.28. | NEW | ITT | Adverse Events of Special Interest by Category - On Study (Year 1&2) | 
 New output (omission in original RAP) |
| 23.29. | 23.31 | ITT | Malignant Neoplasm Adverse Events of Special Interest by Category and PT - On Study (Year 1&2) | 
 Now presents data for Year 1&2 |
| 23.30. | 23.32 | ITT | Post Belimumab SC Injection Systemic Reactions Adverse Events of Special Interest by Category and PT - On Study (Year 1&2) | 
 Now presents data for Year 1&2 |
| 23.31. | 23.33 | ITT | Serious Post Belimumab SC Injection Systemic Reactions Adverse Events of Special Interest by Category and PT - On Study (Year 1&2) | 
 Now presents data for Year 1&2 |

| Safety Tables | | | | |
|---|-------------------|------------|---|--|
| New output number | Old output number | Population | Title | Major modifications since original RAP |
| 23.32. | 23.34 | ITT | Infection Adverse Events of Special Interest by Category and PT - On Study (Year 1&2) | 
 • Now presents data for Year 1&2 |
| 23.33. | 23.35 | ITT | Infection Adverse Events of Special Interest Leading to Belimumab SC Study Treatment Discontinuation by Category and PT - On Study (Year 1&2) | 
 • Now presents data for Year 1&2 |
| 23.34. | 23.36 | ITT | Depression/Suicide/Self-injury Adverse Events of Special Interest by Category and PT - On Study (Year 1&2) | 
 • Now presents data for Year 1&2 |
| 23.35. | 23.41 | ITT | Adverse Events of Special Interest including Exposure-Adjusted Incidence Rates by Category – On Study (Year 1&2) | 
 • Now presents data for Year 1&2 |
| COVID-19 Pandemic Adverse Events | | | | |

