15.3. Appendix 3: Assessment Windows

15.3.1. Definitions of Assessment Windows for Analyses

The data is analyzed as per the planned visit assignment.

Exit/withdrawal and unscheduled visits will be slotted to the appropriate planned visit. The assigned visit is based on the interval in which the Study Day for the exit/withdrawal or unscheduled visit falls according to intervals (inclusive) provided below. For completeness, the table also includes visits which are not slotted; these visits will have 'na' for 'not available' listed for the Interval Start and End Day.

| Analysis Set / Domain | Parameter (if applicable) | Target ¹ | Analysis Window | | Analysis Timepoint Number ⁴ | Analysis Timepoint |
|---------------------------------------|---------------------------|---------------------|---------------------|---------------------------|--|--------------------|
| | | | Beginning Timepoint | Ending Timepoint | | |
| All | All | NA | NA | NA | 10 | Screening |
| Year 1 Treatment Phase visits: | | | | | | |
| All | All | 1 | NA | NA | 20 | Baseline |
| | | 29 | 2 | 35 | 30 | Week 4 |
| | | 43 | 36 | 49 | 40 | Week 6 |
| | | 57 | 50 | 70 | 50 | Week 8 |
| | | 85 | 71 | 98 | 60 | Week 12 |
| | | 113 | 99 | 126 | 70 | Week 16 |
| | | 141 | 127 | 154 | 80 | Week 20 |
| | | 169 | 155 | 175 | 90 | Week 24 |
| | | 183 | 176 | 189 | 100 | Week 26 |
| | | 197 | 190 | 210 | 110 | Week 28 |
| | | 225 | 211 | 238 | 120 | Week 32 |
| | | 253 | 239 | 266 | 130 | Week 36 |
| | | 281 | 267 | 294 | 140 | Week 40 |
| | | 309 | 295 | 322 | 150 | Week 44 |
| | | 337 | 323 | 350 | 160 | Week 48 |
| 365 | 351 | 392 | 170 | Week 52 | | |
| 365 | na | Na | 175 | Survival-W52 ² | | |
| Year 2 Phase Visits: | | | | | | |
| All | All | 421 | 393 | 434 | 180 | Week 60 |
| | | 449 | 435 | 476 | 190 | Week 64 |
| | | 505 | 477 | 532 | 200 | Week 72 |
| | | 561 | 533 | 588 | 210 | Week 80 |
| | | 617 | 589 | 644 | 220 | Week 88 |
| | | 673 | 645 | 700 | 230 | Week 96 |
| | | 729 | 701 | 742 | 240 | Week 104 |

| Analysis Set / Domain | Parameter (if applicable) | Target ¹ | Analysis Window | | Analysis Timepoint Number ⁴ | Analysis Timepoint |
|-----------------------|---------------------------|---------------------|---------------------|------------------|--|----------------------------|
| | | | Beginning Timepoint | Ending Timepoint | | |
| | | 729 | na | na | 245 | Survival-W104 ² |
| | | Na | na | na | 250 | Follow-Up ³ |

NOTES:

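### RAP 8.1.5: the belimumab day 0 to +3 reaction window overlaps the infusion window, and no rule allocates events that fall in both

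*SAP*

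**What the plan says.** RAP 8.1.5 presents post-injection systemic reactions by treatment group, "by the first six injections and over all injections". T13.35 (all) and T13.36 (serious) use the CMQ broad search with the window "on the day of the injection or within 3 days after the Belimumab injection) by PT in the first six injections". T13.40 uses the same search with the window "on the day of the injection or within 3 days after the Rituximab infusion) by PT". T13.33 and T13.34 give the reaction categories listed in RAP 8.1.4: three are CMQ searches (narrow, broad, algorithmic) and the rest are serious events classified by sponsor adjudication. T13.37 to T13.39 are also adjudicated.

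The second RAP addendum (Section 2.1.7) carries T13.33 and T13.34 into the final report as 23.30 and 23.31. The first is headed "Post Belimumab SC Injection Systemic Reactions Adverse Events of Special Interest by Category and PT - On Study (Year 1&2").

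On dosing, the Protocol Synopsis states: "Belimumab will be administered SC on Day 1 and then weekly (i.e., every 7 days ±1 day"), and "Rituximab-placebo or rituximab will be administered by intravenous (IV) infusions at Weeks 4 and 6 for Arms A and B". For the case where an injection and an infusion would share a day, Protocol Section 2, Table 1, footnote s asks sites to shift the injection if they can: "the day of the belimumab injection should be altered within the dosing window to separate the day of the injection from the day of the" (the sentence goes on to name the infusion).

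**The concern.** A window of four days after every weekly injection is likely to take in events that follow an infusion. The CMQ search picks events by preferred term and date, not by suspected agent. If nothing directs an event that lies in both windows, an infusion reaction to rituximab meets the criteria for a table whose title names belimumab, and the same event also meets those for T13.40.

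Agent attribution matters in this trial. Protocol 3.3.1 names increased hypersensitivity with co-administration as a risk. Protocol 5.4.1 gives, as one reason for infusing at Weeks 4 and 6, that staggering the two starts lets safety events be traced to the agent being started. A first-six-injection table that pools injections before and after the first infusion does not use that stagger.

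**Working it through.** **Inputs.** Belimumab: Day 1, then every 7 days ±1 (Protocol Synopsis). Infusions: Weeks 4 and 6, Arms A and B. Target days: RAP 15.3.1, where the Week 4 row reads "29 | 2 | 35 | 30 | Week 4" (the first number is the target day) and the Week 6 target is 43. Event window: day 0 to +3, which is 4 calendar days. Visit window ±7 days from Week 4, and second infusion 2 to 3 weeks after the first (Protocol Section 2, Table 1, footnotes a and j).

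**1. Target days reproduced.** Day = 1 + 7 × week. Week 4: 1 + 28 = 29. Week 6: 1 + 42 = 43. Both match the RAP.

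**2. Nominal injection days.** Injection k = 1 + 7(k − 1), giving Days 1, 8, 15, 22, 29, 36 and 43 for injections 1 to 7.

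**3. Which tables reach which infusion.**
- First six injections: the window of injection 5 is Days 29 to 32, so it contains the Week 4 infusion. The window of injection 6 is Days 36 to 39, which ends 4 days before Day 43. The Week 6 infusion is outside.
- All injections: the window of injection 7 is Days 43 to 46, so both infusions are inside.

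**4. Effect of footnote s**, for the Week 4 infusion window (Days 29 to 32):

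| Injection 5 given on | Belimumab window | Infusion-window days covered |
|---|---|---|
| Day 28 | 28 to 31 | 29, 30, 31 (3 of 4) |
| Day 29 | 29 to 32 | 29, 30, 31, 32 (4 of 4) |
| Day 30 | 30 to 33 | 30, 31, 32 (3 of 4) |

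The same holds for injection 7 and Days 43 to 46. Moving the injection to the day after takes the infusion day itself out of the belimumab window; moving it to the day before does not.

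**5. When the infusion is not on the injection day.** With exact 7-day spacing, 7 − 4 = 3 days per cycle are uncovered, fewer than the 4 days of an infusion window, so some overlap is unavoidable. If the ±1 day allowance stretches one gap to 8 days, 4 days are uncovered and an infusion window could just fit. Off-schedule overlap is therefore usual, not certain.

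**6. Can Week 6 enter the first-six tables?** The first infusion may be on Days 22 to 36 (15 days) and the second 14 to 21 days later (8 values): 15 × 8 = 120 combinations. With injections on their nominal days, the second infusion falls on Days 36 to 39 in 4 + 3 + 2 + 1 = 10 of them, or 8%. This is a count of permitted timings, not a forecast. It also happens if one earlier injection was missed, because Day 43 is then the sixth injection. Conversely, a first infusion on Day 22 coincides with injection 4. Injection number is therefore an unreliable marker of infusion exposure; the infusion date is needed.

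**7. Allocation rule.** RAP 8.1.4 and 8.1.5 and both addenda contain none.

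**The case against.** The strongest reply is that these tables show temporal association and that causality is handled elsewhere. Treatment-related events are tabulated separately for belimumab only, rituximab only and both (T13.07 to T13.09; 23.06 to 23.08 in the final report), with parallel tables for serious events. T13.40 shows the infusion window in its own right. Arm A receives placebo infusions at the same weeks with the same premedication, so a B-over-A excess can already be read as the effect of adding rituximab. The serious tables T13.37 to T13.39 are adjudicated. The AESI categories come from the Program Safety Analysis Plan, which is not among these documents and might hold an attribution rule. Finally, taking events with overlapping exposure out of the belimumab rows could hide the joint risk that the protocol is concerned about.

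Most of this stands and narrows the point. It leaves T13.40 and the adjudicated tables alone, and it rules out any fix that removes events. It does not close the gap. The relatedness tables are separate displays, and 8.1.5 does not say that the CMQ rows use relatedness. Arm A helps with B against A, but Arm C has no infusion, so B against C mixes the two agents under a belimumab heading. The RAP cites the Program Safety Analysis Plan for categories and adjudication, not for allocation between two dosing windows.

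A reader might also infer that the second addendum dropped a rituximab-window table from the final report. It did not: the RAP specified T13.40 for Year 1 on-treatment reporting only, with no end-of-study counterpart.

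**Conclusion.** The overlap is real and follows from the plan's own schedule. Nominally it covers the Week 4 infusion in T13.35 and T13.36, and both infusions in T13.33, T13.34, 23.30 and 23.31. When an injection is due on the infusion day, 3 or 4 of the 4 infusion-window days lie inside the belimumab window. With no allocation rule, CMQ-matching rituximab infusion reactions in Arm B can be shown as post-belimumab reactions. This rests on the nominal schedule and on the absence of such a rule in the Program Safety Analysis Plan, which could not be checked.

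Three stronger readings are tempting and not supported:
- That infusion reactions will be counted as belimumab reactions. Only events matching the query enter, and an injection given the day after the infusion leaves infusion-day events out.
- That the first-six tables span both infusions. On the nominal schedule they reach Week 4 only.
- That a number of misplaced events can be given. The documents state no rate of infusion-day reactions. Turning 4-in-7-day coverage into an expected count would require injection and infusion days to be unrelated, which the weekly schedule and footnote s contradict.

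The consequence is limited to descriptive safety tables. No efficacy test or estimand is touched.

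**What to change.** In the CMQ-based rows of T13.33 to T13.36 and of 23.30 and 23.31, keep the total and split it, using actual infusion dates, into:

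- (a) events before the first infusion (for Arm C, before the nominal Week 4 day), as the belimumab-only comparison across arms;
- (b) events from an infusion day to +3 days, labelled as falling in both windows;
- (c) all other events.

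Add a footnote that row (b) overlaps T13.40. Leave the adjudicated tables T13.37 to T13.39 unchanged.

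The cost is a paragraph of RAP wording and one derived flag from dates already collected. The second addendum was written after the first database lock, so the Year 1 tables would need a supplementary run. Tables 23.30 and 23.31 cover both years and can carry the split in the final report. The downside is small: a true belimumab reaction close to an infusion appears in row (b), but it stays in the total.

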9.4. Assessments at Unscheduled Visits

Unscheduled visits may be performed for a variety of reasons, including safety. The specific procedures to be performed at an Unscheduled Visit depend on the reason for the

Unscheduled Visit. Additional information on the procedures to be performed at an Unscheduled Visit is provided in the SRM.

Note: if a subject is unable to attend their scheduled visit, for example as a consequence of restrictions related to the COVID-19 pandemic, for continued safety monitoring, the investigator should contact the subject by telephone or video call to review adverse events (including suicidal ideation/behavior and neurological symptoms), concomitant medications and ongoing SLE treatments including belimumab. These reviews will be documented in the source records and the eCRF. Such telephone/video contacts may be recorded as unscheduled visits. No attempt should be made to perform efficacy assessments at these telephone/video contacts.

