| 23.36. | 23.42 | ITT | Exposure Adjusted Incidence Rates of Adverse Events Over Time in Relation to COVID-19 Pandemic – On Study (Year 1&2) | 
 • Now presents data for Year 1&2 |
| Columbia-Suicide Severity Rating Scale (C-SSRS) | | | | |
| 23.37. | 23.45 | ITT | C-SSRS Suicidal Ideation or Behavior during On Study Period (Year 1&2) | 
 • Now presents data for Year 1&2 |
| 23.38. | 23.46 | ITT | Treatment-Emergent C-SSRS Suicidal Ideation or Behavior On Study Relative to Pre-treatment (Year 1&2) | 
 • Now presents data for Year 1&2 |
| Laboratory Results | | | | |
| 23.39. | 23.50 | ITT | Worst Post-Baseline Laboratory Toxicity Grade: Hematology (Year 1&2) | 
 • Now presents data for Year 1&2 |
| 23.40. | 23.51 | ITT | Laboratory Toxicity Grade Worsening of at Least 2 Grades from Baseline: Hematology (Year 1&2) | 
 • Now presents data for Year 1&2 |
| 23.41. | 23.54 | ITT | Worst Post-Baseline Laboratory Toxicity Grade: Liver Function (Year 1&2) | 
 • Now presents data for Year 1&2 |

| Safety Tables | | | | |
|--------------------------|--------------------------|-------------------|--|---|
| New output number | Old output number | Population | Title | Major modifications since original RAP |
| 23.42. | 23.55 | ITT | Laboratory Toxicity Grade Worsening of at Least 2 Grades from Baseline: Liver Function (Year 1&2) | • Now presents data for Year 1&2 |
| 23.43. | 23.58 | ITT | Worst Post-Baseline Laboratory Toxicity Grade: Electrolytes (Year 1&2) | • Now presents data for Year 1&2 |
| 23.44. | 23.59 | ITT | Laboratory Toxicity Grade Worsening of at Least 2 Grades from Baseline: Electrolytes (Year 1&2) | • Now presents data for Year 1&2 |
| 23.45. | 23.62 | ITT | Worst Post-Baseline Laboratory Toxicity Grade: Other Chemistries (Year 1&2) | • Now presents data for Year 1&2 |
| 23.46. | 23.63 | ITT | Laboratory Toxicity Grade Worsening of at Least 2 Grades from Baseline: Other Chemistries (Year 1&2) | • Now presents data for Year 1&2 |
| 23.47. | 23.65 | ITT | Worst Post-Baseline Laboratory Toxicity Grade: Urinalysis (Year 1&2) | • Now presents data for Year 1&2 |
| 23.48. | 23.66 | ITT | Laboratory Toxicity Grade Worsening of at Least 2 Grades from Baseline: Urinalysis (Year 1&2) | • Now presents data for Year 1&2 |

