5.12. On Treatment

For Year 1 on treatment is defined as from 1st dose of belimumab to the latter of: last dose of belimumab + 28 days or last dose of rituximab + 28 days

For Year 1&2 arm C, on treatment is defined as from 1st dose to last dose of belimumab + 28 days.

For Year 2 Arms A&B on treatment is not defined as there is no on treatment reporting (as all subjects are off treatment)

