7. EFFICACY ANALYSES

The primary objective of the study is to demonstrate superiority (improvement in response rate) of co-administration of belimumab plus rituximab (Arm B: Combination) over belimumab monotherapy (Arm A: Control), when comparing the primary efficacy endpoint at Week 52 in subjects with SLE.

An exploratory summary of Arm B (Combination) vs Arm C (Reference) will also be shown.

SLEDAI-2K score has been measured by both the principal investigator (PI) and the independent blinded assessor (IBA). The key differences between these assessments is the frequency of assessment and awareness of the treatment allocation for Arm C:

- The principal investigator conducts a SLEDAI-2K assessment every 4 weeks in Year 1 (at least every 8 weeks in Year 2), whereas the independent blinded assessor conducts a SLEDAI-2K assessment at a reduced set of key time points (weeks baseline, 12, 26, 40, 52, 64, 80, and 104).
- The principal investigator knows which of their subjects are randomised to treatment arm C, but does not know if their remaining subjects are randomised to arm A or arm B. The independent blinded assessor however is not aware of any MITT population subject's treatment randomisation (Section 4).

Due to the level of blinding the primary and major secondary efficacy endpoints will be conducted using the independent blinded assessors' SLEDAI-2K assessment. Note however the PI assessment of SLEDAI-2K at baseline, is used as the baseline covariate in all adjusted analysis (the baseline SLEDAI-2K assessment is conducted prior to randomisation).

The other secondary endpoints analysis utilises the greater visit frequency of the principal investigator assessment. This is particularly pertinent for differentiating between treatments when considering time to response or duration of response. In by visit summaries, it also allows for the assessment of fluctuating response.

The primary and major secondary efficacy endpoints are repeated using the principal investigator assessment.

Details of the planned displays are provided in Section 15.11 and are based on GSK data standards and statistical principles. Listings of all key efficacy endpoints will be provided [L12.01 – L12.02, and L22.01-L22.02].

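### Final-report table 23.36 pools Years 1 and 2 in its pre- versus during-pandemic adverse-event rates, so pandemic phase is heavily confounded with study year

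*SAP*

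**What the plan says.** RAP section 8.1.6 adds adverse-event summaries meant to clarify the safety profile, the effect of the pandemic on safety, or both. It states: "Event rates will be reported by calendar time defined as either pre or during the COVID-19 pandemic", with a later phase added if an end date is set. It specifies two sets of tables.

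- **Year 1 set (T13.49-T13.51).** "The following Tables will summarise the Year 1 On Treatment (Section 5.12) events for pre or during the COVID-19 pandemic".
- **Combined set (T23.42-T23.44).** "The following Tables will summarise the Year 1 and 2 combined On-Study (Section 5.11) events for pre or during the COVID-19 pandemic". The only adjustment is this: "Event rates will be adjusted for on-study exposure in the relevant pandemic phase".

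The second RAP addendum (section 2.1.7) keeps one table of the combined set, as 23.36: "Exposure Adjusted Incidence Rates of Adverse Events Over Time in Relation to COVID-19 Pandemic". It covers Years 1 and 2, with no split by study year. Old T23.43 and T23.44 are not in the addendum's list.

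On drug status, RAP section 5.12 says: "For Year 2 Arms A&B on treatment is not defined as there is no on treatment reporting". Protocol section 5.1 keeps Arm C on belimumab through Week 104, and Protocol section 7.7.4 lets some Arm A and B participants continue or restart belimumab in Year 2.

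**The concern.** A pre/during comparison informs about the pandemic only if the two phases are otherwise alike. Dividing by exposure corrects for how long people were observed in each phase. It does not correct for which part of the study they were in. In this trial three things move with study year:

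- **Drug exposure.** Arms A and B finish belimumab at the end of Year 1; Arm C does not. Any distortion can therefore differ by arm.
- **Early events.** The Week 4 and Week 6 infusions and the immunosuppressant withdrawal by Week 4 all fall early in Year 1.
- **Visit frequency.** The schedules of activities have fewer visits, and so fewer scheduled adverse-event reviews, in Year 2.

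If pandemic phase largely coincides with study year, a change in rates in 23.36 cannot be attributed to the pandemic. A real pandemic change could also be hidden by an opposite change between years.

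**Working it through.** RAP section 8.1.6 gives no figure to reproduce, so the check is of the person-time split.

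**Inputs**
- First randomisation: about March 2018 (RAP section 3.1 puts the first IDMC review in September 2018, six months after it). Taken as 15 March 2018.
- Onset: 10 February 2020 for 8 of 11 countries; 25 February to 13 March 2020 for the other three (RAP section 15.6.16). Taken as 10 February 2020.
- Last randomisation: not stated. Assumed between 31 March and 8 October 2019. The first RAP addendum, dated 8 October 2020, still precedes the Year 1 database release.
- Accrual uniform and no dropout (assumptions). Each study year is 364 days.
- Post-baseline visits, from the schedules: Weeks 4, 6, 8, 12, 16, 20, 24, 26, 28, 32, 36, 40, 44, 48 and 52 (15) in Year 1; Weeks 60, 64, 72, 80, 88, 96 and 104 (7) in Year 2.

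**Person-time**

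Let c be a participant's days in study at onset. It is uniform between L (last entrant) and 697 (first entrant, 15 March 2018 to 10 February 2020). Since 697 < 728, nobody reaches Week 104 before onset, which agrees with RAP section 9. Mean days per participant are:

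- pre-pandemic total = (L + 697)/2
- Year 1 during = (364 - L)² / [2(697 - L)]
- Year 1 pre = 364 - Year 1 during
- Year 2 pre = pre-pandemic total - Year 1 pre
- Year 2 during = 728 - pre-pandemic total - Year 1 during

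| Last entry | L | Year 1 pre | Year 2 pre | Year 1 during | Year 2 during | Year 1 share of pre | Year 2 share of during |
|---|---|---|---|---|---|---|---|
| 31 Mar 2019 | 316 | 361.0 | 145.5 | 3.0 | 218.5 | 71% | 99% |
| 30 Jun 2019 | 225 | 343.5 | 117.5 | 20.5 | 246.5 | 75% | 92% |
| 8 Oct 2019 | 125 | 314.1 | 96.9 | 49.9 | 267.1 | 76% | 84% |

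Example, L = 125: pre total (125 + 697)/2 = 411; Year 1 during 239²/(2 × 572) = 49.9; Year 1 share of pre 314.1/411 = 76%; Year 2 share of during 267.1/317 = 84%.

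Even with the latest entry date, the last participant is at Week 125/7 = 17.9 at onset, so all scheduled infusions are pre-pandemic. Scheduled visits per patient-year are 12.5-13.0 pre and 7.7-8.5 during.

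A variant that places 29/70 of accrual before 7 September 2018 (the 29 affected Arm C participants out of 70 planned), ends accrual between 31 May and 8 October 2019 and allows 0% or 15% dropout gives 73-75% and 84-95%.

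**Ratio with no pandemic effect**

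Let r be the Year 2/Year 1 rate ratio in an arm, a the Year 1 share of pre time, and b the Year 1 share of during time. Then during/pre = [b + (1 - b)r] / [a + (1 - a)r]. For L = 316 and r = 0.7 this is (0.0136 + 0.9864 × 0.7)/(0.7127 + 0.2873 × 0.7) = 0.704/0.914 = 0.77.

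| r | during/pre across the three entry dates |
|---|---|
| 0.5 | 0.59-0.66 |
| 0.7 | 0.77-0.80 |
| 0.9 | 0.93-0.94 |
| 1.0 | 1.00 |
| 1.25 | 1.14-1.16 |

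Within one study year the no-effect ratio is r/r = 1.00 for any r, provided the rate is constant within that year.

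**The case against.** The strongest reply is that 23.36 is one supplementary descriptive table. Section 8.1.6 plans no ratio, interval or test, and its stated purpose is wider than the pandemic effect. The final report also has Year 2-only adverse-event tables (23.01, 23.03, 23.18, 23.27) and outputs on pandemic visit disruption (Table 21.12, Figure 21.03, Listing 21.09). All of this is correct, and it limits the importance of the point. But none of those outputs separates pre from during within a year, so they do not supply the missing comparison.

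A reader might infer four stronger things that the documents do not support.

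- **That all the pandemic tables mix study years.** T13.49-T13.51 are limited to Year 1 on-treatment events. What remains there is only time since randomisation within Year 1, a narrower matter.
- **That 23.36 must show a spurious change.** It does so only if recorded rates differ between years. No rates are given, and the direction is open: Year 2 permits restarted belimumab, higher corticosteroid doses and immunosuppressants, which could raise rates.
- **That fewer visits must mean fewer recorded events.** Adverse events are collected continuously and serious ones reported within 24 hours (Protocol section 9.7.1). When a visit cannot be attended, Protocol section 9.4 says "the investigator should contact the subject by telephone or video call to review adverse events". Visit frequency is a difference between phases, not proven under-reporting.
- **That the comparison of arms is biased.** Arms compared within one phase share essentially the same mix of study years.

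**Conclusion.** The point holds for table 23.36 only. Pandemic phase is heavily confounded with study year: 71-76% of pre-pandemic time is Year 1 and 84-99% of pandemic time is Year 2. The two are not identical, since 24-29% of pre-pandemic time is Year 2. Exposure adjustment does not remove the confounding. The size of any resulting artefact is unknown because it depends on r: modest at 0.9, about a fifth at 0.7, absent at 1.0 and reversed at 1.25.

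The shares rest on an assumed accrual shape and end date and a single onset date; the calibrated variant with dropout leads to the same conclusion. This is an inexpensive improvement to a descriptive safety table. No primary or secondary efficacy result depends on it.

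**What to change.** In a short RAP addendum, present 23.36 by study year within arm (Year 1 pre and during, Year 2 pre and during), with person-years shown in every cell. Leave T13.49-T13.51 unchanged. No model is needed.

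The cost is one re-cut of existing data. The drawback is a small Year 1 during cell. For a 70-participant arm with no dropout it holds 3.0 × 70/365.25 = 0.6 to 49.9 × 70/365.25 = 9.6 person-years, and it should be labelled as sparse. It also starts no earlier than about Week 18, so the Year 1 contrast still sets early against late Year 1.

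The Year 2 contrast is better filled: 96.9 to 145.5 days per participant pre and 218.5 to 267.1 during, or about 19-28 and 42-51 person-years per 70-participant arm. It is the one to read for a pandemic effect.
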